10.4 ADDITIONAL EFFICACY PARAMETERS

11.0 SAFETY ANALYSES

The safety analysis will be performed using the safety population. The safety parameters will include the following nonocular safety parameters: nonocular AEs, clinical laboratory values, vital signs, and pregnancy; and ocular safety parameters: ocular AEs, implant/sham assessment, visual acuity, visual field examination, macroscopic iris color assessment, macroscopic conjunctival hyperemia assessment, Bimatoprost SR implant assessment, biomicroscopic examination, lens assessment, optic disc examination, dilated ophthalmoscopic examination, gonioscopy assessment, optical coherence tomography (OCT), specular microscopy, pachymetry, anterior segment optical coherence tomography (AS-OCT). Unless otherwise stated, the last nonmissing safety assessment before the first dose of study treatment will be used as the baseline for all analyses of that safety parameter. Continuous variables will be summarized by number of patients and mean, SD, median, the 1st quartile and the 3rd quartile, minimum, and maximum values. Categorical variables will be summarized by number and percentage of patients.

For ocular safety assessments, analyses will be performed by treatment group for study eye and pooled for fellow eye based on the first actual treatment received in each eye. For nonocular safety measures, analyses will be performed on a patient basis for the treatment actually received.

For all safety by-cycle summary analyses, in order to compare cycles of similar duration, the data included in each cycle will be,

- Cycle 1 (16 weeks): data from the 1st injection to the 2nd injection date -1 or upper bound of week 15 visit window (section 16.1) if a patient didn't receive the 2nd injection;
- Cycle 2 (16 weeks): data from the 2nd injection to the 3rd injection date -1 or upper bound of week 31 visit window (section 16.1) if a patient didn't receive the 3rd injection;
- Cycle 3 (20 weeks): data from the 3rd injection to upper bound of week 52 visit window (section 16.1);
- Extended safety follow up: data after week 52 for patients with 3 injections and extended follow up.

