11.1 ADVERSE EVENTS

Adverse events will be coded by SOC and preferred term using the Medical Dictionary for Regulatory Activities.

For a given AE and patient, if more than 1 severity grade is reported, the worst severity grade (the greater of the onset and maximum severity recorded on the electronic case report from [eCRF]), will be used for analysis.

Adverse events will be classified into ocular AEs and nonocular AEs. An ocular AE will be determined as indicated on the AE form of eCRF, and thus are not limited to AEs with primary SOCs of eyes. The treatment-related ocular AEs will be further broken down by either related to injection procedure or related to study drug as indicated on eCRF. Ocular AEs will be tabulated by treatment group for the study eye and pooled for the fellow eye, and nonocular AEs will be summarized by treatment group for patient. Analysis by cycle of treatment will also be performed.

Treatment-Emergent Adverse Events

An AE will be considered a treatment-emergent adverse event (TEAE) for the study treatment period if the AE meets 1 of the following criteria:

- The onset date is on or after the first study treatment date.
- The onset date is before the first study treatment date and either:
 - The severity of the event worsened on or after the first treatment date.
 - The event became serious on or after the first study treatment date.

An AE will be considered as a TEAE for a treatment cycle if the AE meets 1 of the following criteria:

- The onset date is on or after the treatment administration of the cycle but prior to the next cycle administration.
- The onset date is before the treatment administration of the cycle and either:
 - The severity of the event worsened on or after the treatment administration of the cycle.
 - The event became serious on or after the treatment administration of the cycle.

Overall summary of TEAEs will be provided on a per-patient basis for categories of all TEAEs, treatment-related TEAEs, injection procedure-related TEAEs, study drug-related TEAEs, serious TEAEs (STEAEs), deaths, and TEAEs leading to study discontinuation. Each category (except deaths) will be further classified into ocular and nonocular subcategories.

The number and percentage of patients reporting TEAEs will be provided on a per-patient basis by 1) SOC and preferred term; 2) SOC, preferred term and severity in descending order of frequency for each treatment group.

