11.3.2 Best Corrected Visual Acuity

Best corrected visual acuity (BCVA) will be measured for both eyes using the logMar chart at all scheduled visits except on the 3 administration days. BCVA will be recorded in Snellen equivalent units. The line change from baseline at each follow-up evaluation will be calculated using the following formula:

$$\text{Line change} = 10 \times [\log_{10} (20/d_{\text{follow-up}}) - \log_{10} (20/d_{\text{baseline}})]$$

where d_{baseline} = denominator of the Snellen equivalent unit at baseline,
 $d_{\text{follow-up}}$ = denominator of the Snellen equivalent unit at follow-up

The logarithmic values are to be rounded to the nearest tenth before calculation of the line change. A positive value indicates an improvement and a negative value indicates a worsening. For example, the line change for a Snellen equivalent unit at baseline of 20/25 followed by a Snellen equivalent unit of 20/80 at follow-up would be the following:

$$\text{Line change} = 10 \times [\log_{10}(20/80) - \log_{10} (20/25)] = 10 \times (0.1 - 0.6) = -5$$

which represents a worsening of 5 lines in visual acuity.

The data for the worst line change from baseline across follow-up will be summarized by treatment group for study eye and pooled for fellow eye. The worst line change is defined as the greatest decrease from baseline in the number of lines read. Summary statistics of the worst line change will be presented in each of the following categories: worsening (< -2), no changes (≥ -2 and ≤ 2), and improving (> 2). The number and percentage of patient eyes in each category will be presented. Similar analyses will be conducted by treatment cycle.

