11.3.4 Macroscopic Conjunctival Hyperemia Assessment

Macroscopic conjunctival hyperemia assessment will be performed for each eye at all scheduled visits except on any of the 3 administration days using the following scale: 0 = none, +0.5 = trace, +1 = mild, +2 = moderate, and +3 = severe. The frequency distribution for the severity grade at each scheduled visit will be summarized by treatment group for the study eye and pooled for the fellow eye.

To summarize findings from macroscopic conjunctival hyperemia assessment, a tabulation of the number and percentage of patient eyes who had more than 1 severity grade increase (worsening, i.e., a change from 0 to 2 and above, from 0.5 to 2 and above, or from 1 to 3 and above) from the baseline at any of the follow-up visits will be summarized. Similar analyses will be performed for each treatment cycle and may be provided for findings with other severity grade increase.

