16.3 REPEATED OR UNSCHEDULED ASSESSMENTS OF SAFETY PARAMETERS

If a patient has repeated assessments before the start of the first treatment, unless otherwise stated, the results from the final nonmissing assessment made prior to the start of the study treatment will be used as baseline. If end-of-study assessments are repeated or if unscheduled visits occur, the last nonmissing postbaseline assessment will be used as the end-of-study assessment for generating summary statistics. However, all postbaseline assessments will be used for safety evaluation, and all assessments will be presented in the data listings.

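### By-cycle tables of visual acuity, hyperemia and slit-lamp/fundus findings use the pre-treatment baseline, so a finding that persists in a re-dosed eye is counted again in later cycles

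*SAP*

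**What the plan says.** **Baseline.** SAP 11.0 sets one default, which may be overridden where another rule is stated: the last value before the first dose "will be used as the baseline for all analyses of that safety parameter". SAP 16.3 repeats it for repeated assessments: "the results from the final nonmissing assessment made prior to the start of the study treatment will be used as baseline".

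**Cycle windows.** SAP 11.0 also defines which data belong to each cycle, so that periods of like length can be compared. Cycle 2, for example, is "data from the 2nd injection to the 3rd injection date -1", with a cut-off at the Week 31 window if no third injection is given. This limits the follow-up data that enter a cycle. It does not change the reference value.

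**By-cycle examination tables.**
- 11.3.2, visual acuity: "The worst line change is defined as the greatest decrease from baseline in the number of lines read". Worsening means a line change below -2. Then: "Similar analyses will be conducted by treatment cycle".
- 11.3.4, hyperemia: eyes whose grade rises by more than 1 from baseline at any follow-up visit. Then: "Similar analyses will be performed for each treatment cycle".
- 11.3.5, biomicroscopy and ophthalmoscopy: the same grade rule, or absent at baseline and present later for ungraded findings, again repeated for each cycle.
- 11.3.3, visual field: normal at baseline and abnormal later, tabulated by cycle and over the whole study.

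None of these sections names a cycle-specific baseline.

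**By-cycle adverse events.** SAP 11.1 ties the event to the cycle's own administration: "The onset date is on or after the treatment administration of the cycle but prior to the next cycle administration". An event with earlier onset counts in the cycle only if it worsens or becomes serious after that administration.

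**The concern.** The study objective (Protocol 2.1, SAP 5.0) covers safety after initial and repeated administrations. A reader will look at the by-cycle tables to see whether the second and third implants bring more harm than the first. With a single pre-treatment reference, an eye that acquires a lasting finding or acuity loss in Cycle 1, is dosed again and is still affected at a later visit meets the criterion again in Cycles 2 and 3.

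The examination tables then answer a different question from the adverse event tables printed under the same cycle headings. One persisting finding can appear once among the by-cycle adverse events and three times among the by-cycle examination findings, and the SAP asks for no label that would explain the difference.

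**Working it through.** **1. Reproduce the SAP's figure.** The only number tied to this point is the acuity example in 11.3.2. The line change is 10 × [log10(20/d at follow-up) − log10(20/d at baseline)], with each log rounded to one decimal. For 20/25 to 20/80, the logs are −0.1 and −0.6, so the change is 10 × (−0.6 − (−0.1)) = −5. This matches the SAP. (The SAP prints the two logs without their signs; the answer is the same.)

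**2. Apply the by-cycle rules to a finding that appears in Cycle 1 and stays.**

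| Eye | Reference | Cycle 1 | Cycle 2 | Cycle 3 | Cycles counted |
|---|---|---|---|---|---|
| Acuity 20/25, then 20/80 throughout | pre-treatment | −5 | −5 | −5 | 3 |
| same | start of cycle | −5 | 0 | 0 | 1 |
| Hyperemia 0, then 2 throughout | pre-treatment | +2 | +2 | +2 | 3 |
| same | start of cycle | +2 | 0 | 0 | 1 |
| Ungraded finding, absent then present | pre-treatment | yes | yes | yes | 3 |
| same | start of cycle | yes | no | no | 1 |

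**3. Illustrate the size.** The documents give neither a risk nor a persistence rate, so both are assumed. Let q be the new-onset risk per cycle among unaffected eyes and s the share of findings that last into the next cycle, with every eye re-dosed and examined. The proportion counted against pre-treatment is P(k) = s·P(k−1) + [1 − s·P(k−1)]·q, with P(0) = 0.

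For q = 3%:
- s = 1: P(k) = 1 − 0.97^k, which gives 3.0%, 5.9% and 8.7%. New onsets are 3.0%, 0.97 × 3% = 2.9% and 0.97² × 3% = 2.8%.
- s = 0.5: Cycle 2 is 1 − 0.97 × (1 − 0.015) = 4.5%. Cycle 3 is 1 − 0.97 × (1 − 0.0223) = 5.2%.
- s = 0: 3.0% in every cycle. The two ways of counting agree.

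As counts, with q = 5%, s = 1 and the planned 170 per group: 8.5, 16.6 and 24.2 eyes counted, against 8.5, 8.1 and 7.7 new onsets.

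With full persistence, the ratio of the Cycle 3 count to Cycle 3 new onsets is (1 − 0.98³)/(0.02 × 0.98²) = 0.0588/0.0192 = 3.06 at q = 2%, and (1 − 0.9³)/(0.1 × 0.9²) = 0.271/0.081 = 3.35 at q = 10%.

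**4. Allow for selective re-dosing.** If every affected eye were left out of the next administration, no finding would carry over and the tables would show q in each cycle, the same as s = 0. The truth lies between that and the full-persistence figures.

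**5. Test a reset baseline on gradual loss.** For acuity 20/20, 20/32, 20/50, 20/80, the change from the start of each cycle is −2, −2, −2, never below −2. Against pre-treatment it is −2, −4, −6, which is worsening in Cycles 2 and 3. A reset reference alone would miss this eye, so both views are needed.

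**6. Check that the data exist.** Acuity and hyperemia are assessed at every scheduled visit except administration days (11.3.2, 11.3.4), and biomicroscopy at every scheduled visit (11.3.5). Weeks 15 and 31 are scheduled visits, so they normally supply the reference. Dilated ophthalmoscopy is scheduled at Weeks 12 and 28 (11.3.5), about four weeks before the Week 16 and Week 32 administrations. Visual field is scheduled at Screening, Baseline, Week 28, Week 52 and Month 20/Exit (11.3.3). Nothing falls between Baseline and Week 28, so a reset before Week 16 would return the same Baseline value.

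**The case against.** A fixed pre-treatment baseline is a legitimate choice for safety: it captures cumulative change and errs toward showing more harm. These tables are descriptive, and no test or decision rule depends on them. New harm in a cycle is already reported elsewhere: SAP 11.1 tabulates ocular events by cycle (also split at 2 days after administration), together with corneal and anterior chamber inflammation events of interest and events leading to discontinuation or implant removal. Hyperemia grade, lens opacity and endothelial cell density are also shown by visit, and the timolol arm is counted under the same rule. Table specifications sit in a separate document (SAP 4.0), where a cycle-specific rule may exist.

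Most of this stands, and it narrows the point. It does not remove it. The adverse event tables do not change what the examination tables mean, and the control arm does not recover per-cycle incidence within a Bimatoprost SR arm. The cycle windows are justified in SAP 11.0 by comparison between cycles, which is the comparison that carry-over distorts. A rule this basic belongs in the SAP text even if a table specification also contains it.

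A reader might infer two stronger things. One is that repeat dosing is bound to look progressively worse. The documents do not support that: the effect vanishes for findings that resolve, and Protocol 5.10 lets the investigator withhold readministration after adverse events or safety concerns, which takes affected eyes out of later cycles. The other is that the plan cannot separate new harm from carry-over at all. The by-cycle adverse event rule shows otherwise.

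**Conclusion.** The point holds for the by-cycle tables in SAP 11.3.2, 11.3.4 and 11.3.5. As written, they report prevalence against the pre-treatment state among eyes dosed and examined in that cycle. They do not report what is new after each implant, and they should not be read beside the by-cycle adverse event tables as if the two counted alike. The by-cycle visual field table (11.3.3) shares the feature, but its schedule allows a remedy only for Cycle 3.

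The size is unknown. It runs from no distortion, if findings resolve or affected eyes are not re-dosed, to a Cycle 3 count about three times the new onsets under full persistence and full re-dosing at assumed risks of 2% to 10%. All risks and persistence rates here are assumptions.

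The efficacy analyses, the whole-study safety tables, which count each eye once, and the by-cycle adverse event tables are not affected. This concerns how repeat-dose safety will be read, and it is worth correcting because the correction needs no new data.

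**What to change.** - **Label.** Title the existing by-cycle tables in 11.3.2 to 11.3.5 as change from pre-treatment baseline, cumulative, observed in the cycle. Keep them.
- **Add new-in-cycle tables** for visual acuity, hyperemia and biomicroscopy. The reference is the last assessment before that cycle's administration, normally Week 15 for Cycle 2 and Week 31 for Cycle 3. State this in SAP 11.0 as an exception to the default baseline.
- **Dilated ophthalmoscopy.** Use the Week 12 or Week 28 examination as the reference. Add a footnote that a finding arising in the following four weeks or so, before dosing, will be counted as new in the next cycle.
- **Visual field.** Reset for Cycle 3 only, with the Week 28 field as the reference and the same footnote. State that the Week 28 result covers Cycles 1 and 2 together.
- **Reading.** Present each new-in-cycle table next to its cumulative counterpart, because a reset baseline alone can miss gradual loss.

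The cost is a few sentences of SAP text, cycle-specific baseline flags in the programs, and one more descriptive table per measure.

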Adverse events will be coded using the Medical Dictionary for Regulatory Activities (MedDRA) and will be summarized for all events regardless of causality and for treatment-related adverse events. Ocular adverse events and safety variables will be tabulated by study eye and fellow eye within each treatment dose strength or group, and nonocular safety variables will be summarized by patient.

[figure not shown]
Sample Size Calculation: The sample size calculation is based on the primary efficacy analysis of the IOP for US FDA review because the sample size based on the primary efficacy analysis for other regions is expected to be smaller. Based on simulations, a sample size of 486 patients (162 per group) will provide approximately 95.1% and 83.5% power to show noninferiority (NI) of Bimatoprost SR 15 µg and Bimatoprost SR 10 µg, respectively, to timolol at all 6 scheduled timepoints based on an NI margin of 1.5 mm Hg and at 3 or more timepoints based on an NI margin of 1.0 mm Hg. Assuming a premature discontinuation rate of 5% within 12 weeks (before the primary database lock), approximately 510 patients (170 per group) are to be enrolled into this study.

Figure 1 Flowchart of Patient Participation

Approval Date: 05-Jun-2018

[figure not shown]
Table 2 Screening through Treatment Day 1

[figure not shown]
Approval Date: 05-Jun-2018

Table 3 Administration Cycle 1 Schedule of Visits and Procedures: Treatment Period Day 2 through Week 12

[figure not shown]

Approval Date: 05-Jun-2018

[figure not shown]
Table 4 Administration Cycle 2 Schedule of Visits and Procedures: Treatment Period Week 15 Through Week 28

[figure not shown]

Approval Date: 05-Jun-2018

[figure not shown]
Approval Date: 05-Jun-2018

[figure not shown]

Approval Date: 05-Jun-2018

Table 6 **Schedule of Visits and Procedures: Extended Follow Up Months 14, 16, 18, and 20**

Approval Date: 05-Jun-2018

Approval Date: 05-Jun-2018

1. Background and Clinical Rationale

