7.3.3 Other Efficacy Analyses

7.3.4 Safety Analyses

The Medical Dictionary for Regulatory Activities (MedDRA) nomenclature will be used to code adverse events. Adverse events will be coded from the verbatim text into preferred term and system organ class (SOC). The number and percent of patients reporting treatment emergent adverse events will be tabulated based on the primary SOC and preferred terms. Summary tables will be generated for all adverse events regardless of causality as well as treatment-related adverse events for the entire study and by treatment cycle.

Other safety variables include vital signs (blood pressure, pulse rate, and temperature) and pregnancy test results. Ocular safety will be evaluated through assessment of visual acuity and visual field; evaluation of macroscopic bulbar conjunctival hyperemia and iris color; assessment of endothelial cell density and corneal thickness; IOP measurement, biomicroscopic and ophthalmoscopic examinations (including gonioscopy with Bimatoprost SR implant assessment, optic disc examination and dilated fundus examination); and OCT of the macula.

Ocular adverse events and safety variables will be tabulated by study eye and fellow eye within each treatment dose strength, and nonocular safety variables will be summarized by patient. A separate summary will be provided for safety events occurring after nonstudy IOP-lowering medication has been initiated.

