The number and percentage of patients reporting nonocular TEAEs in each treatment group will be tabulated by SOC and preferred term. Also the number and percentage of patients reporting treatment-related (including study drug related or injection procedure related) nonocular TEAEs in each treatment group will be tabulated by SOC and preferred term.

Similar analyses will be done for ocular TEAEs including 1) by PT and severity; 2) treatment-related TEAEs by PT for each treatment group by study eye and fellow eye. In addition, similar analyses will be performed for ocular TEAEs by treatment cycle.

Within each treatment cycle, ocular TEAEs identified (onset or worsened) within 2 days of administration and identified more than 2 days of administration of each cycle will be summarized by each treatment group for study eye and pooled for fellow eye.

Serious TEAEs

Nonocular and ocular STEAEs will be summarized by preferred term and treatment group, respectively.

TEAEs Leading to Study Discontinuation

Nonocular TEAEs and ocular TEAEs leading to premature discontinuation of the study will be summarized by preferred term and treatment, respectively.

Similarly, ocular TEAEs leading to premature discontinuation will also be tabulated by treatment group by treatment cycle.

Ocular TEAEs Leading to Study Drug Discontinuation or Regimen Change

Ocular TEAEs leading to study drug discontinuation will be summarized by preferred term and treatment for the entire study period and also for each cycle. Ocular TEAEs leading to study drug discontinuation or regimen change are defined as the ocular TEAEs with action regarding study drug reported as “Discontinued” or “Regimen Changed” on the eCRF AE form.

Ocular TEAEs Leading to Implant Removal

Ocular TEAEs leading to implant removal will be summarized by preferred term and treatment for the entire study period and also for each cycle.

TEAEs of Special Interest

Corneal TEAEs and Anterior chamber inflammation TEAEs of interest will be summarized by preferred term and treatment group, respectively. Similar analyses will be done by treatment cycle. The full list of corneal AEs and Anterior chamber inflammation AEs of interest will be provided prior to each database lock.

Additional subcategory of TEAEs may be analyzed separately, such as for ocular TEAE associated with use of a prostaglandin analog (PGA), etc.

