11.3.12 Specular Microscopy

Endothelial cell density will be assessed using specular microscopy performed on the central cornea for each eye at Screening, Week 12, Week 28, Week 44, Week 52, and Month 20/Exit. At each examination, average endothelial cell density for each eye will be reported by reading center and used for analysis.

Endothelial cell density baseline and changes from baseline, and raw values will be summarized descriptively by visit for each treatment group in study eyes and pooled for the fellow eyes.

In addition, the number and percentage of patient eyes who reported 1) within ± 200 cells/ mm^2 change; 2) $\geq 10\%$ loss; 3) $\geq 20\%$ loss; 4) $\geq 30\%$ loss; 5) $\geq 40\%$ loss; and 6) $\geq 50\%$ loss in endothelial cell density will be summarized by visit for each treatment group in study eyes and pooled for fellow eyes respectively for each category.

Fellow eye-adjusted endothelial cell density changes from baseline and percent loss from baseline values in the study eye are defined below.

- Fellow eye-adjusted endothelial cell density change from baseline (CFB_ADJ) is defined as the difference in endothelial cell density change from baseline between the study eye and the fellow eye, and calculated as $CFB_ADJ = CFB_SE - CFB_FE$, where CFB_SE is endothelial cell density change from baseline in the study eye and CFB_FE is endothelial cell density changes from baseline in the fellow eye.
- Fellow eye-adjusted endothelial cell density percent loss from baseline (PLoss_ADJ) is defined as the difference in endothelial cell density percent loss from baseline between the study eye and the fellow eye, and calculated as $PLoss_ADJ = PLoss_SE - PLoss_FE$, where PLoss_SE is endothelial cell density percent loss from baseline in the study eye and PLoss_FE is endothelial cell density percent loss from baseline in the fellow eye.

Fellow eye-adjusted endothelial cell density will be summarized descriptively by visit for each treatment group, and the number of patients who reported changes within ± 200 cells/mm² will also be summarized.

Additionally, the number and percentage of patients who reported 1) $\geq 10\%$ loss; 2) $\geq 20\%$ loss; 3) $\geq 30\%$ loss; 4) $\geq 40\%$ loss; and 5) $\geq 50\%$ loss in fellow eye-adjusted endothelial cell density percent loss will be summarized by visit for each treatment group for each category, respectively.

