16.7.2 Incomplete Stop Date

The following rules will be applied to impute the missing numeric fields for an incomplete prior or concomitant medication stop date unless the stop date is marked as ongoing. If the imputed stop date is before the start date (imputed or nonimputed start date), the imputed stop date will be equal to the start date. If the stop date is marked as ongoing, the study exit date will be assigned to the missing fields. If the study exit date is not available, the last visit date will be used for imputation.

Missing Month and Day

- If the year of the incomplete stop date is the same as the year of the study exit date, the month and day of the study exit date will be assigned to the missing fields.
- If the year of the incomplete stop date is before the year of the study exit date, *December 31* will be assigned to the missing fields.
- If the year of the incomplete stop date is after the year of the study exit date, *January 1* will be assigned to the missing fields.

Missing Month Only

- If only the month is missing, the day will be treated as missing and both the month and the day will be replaced according to the above procedure.

Missing Day Only

- If the month and year of the incomplete stop date are the same as the month and year of the study exit date, the day of the study exit date will be assigned to the missing day.
- If either the year of the incomplete stop date is before the year of the study exit date or if both years are the same but the month of the incomplete stop date is before the month of the date of the study exit date, the last day of the month will be assigned to the missing day.
- If either the year of the incomplete stop date is after the year of the study exit date or if both years are the same but the month of the incomplete stop date is after the month of the study exit date, the first day of the month will be assigned to the missing day.

17.0 **CHANGES TO ANALYSES SPECIFIED IN PROTOCOL**

Two additional terms the time-matched baseline IOP (either Hour 0 or Hour 2 according to the response variable) and timepoint-by-baseline Hour 0 IOP interaction were added to the primary efficacy analysis model, but were not presented in protocol amendment 3, dated 5JUN2018.

18.0 **REFERENCES**

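### The SAP pools fellow eyes across arms for most ocular safety summaries, where the protocol tabulates them within each arm, and does not declare the change.

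*SAP*

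**What the plan says.** The protocol sets the rule twice. The Protocol Summary says: "Ocular adverse events and safety variables will be tabulated by study eye and fellow eye within each treatment dose strength or group". Protocol 7.3.4 repeats it without the last two words: "Ocular adverse events and safety variables will be tabulated by study eye and fellow eye within each treatment dose strength". Only the Summary therefore covers Control explicitly.

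SAP 11.0 sets a different general rule: "analyses will be performed by treatment group for study eye and pooled for fellow eye", with each eye classed by the first treatment that it actually received. SAP 11.1 applies it to adverse events: "Ocular AEs will be tabulated by treatment group for the study eye and pooled for the fellow eye". Pooling of the fellow eye is then restated for ocular events within and beyond 2 days of administration (11.1), visual acuity (11.3.2), hyperemia (11.3.4), biomicroscopy, ophthalmoscopy and lens (11.3.5), cup/disc ratio (11.3.6), pachymetry (11.3.11) and specular microscopy (11.3.12).

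Two parts of the SAP keep fellow-eye information by arm. A later sentence of SAP 11.1 asks for ocular events by preferred term and severity, and "treatment-related TEAEs by PT for each treatment group by study eye and fellow eye". SAP 11.3.12 says: "Fellow eye-adjusted endothelial cell density will be summarized descriptively by visit for each treatment group".

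SAP 17.0, which records changes from the protocol, opens "Two additional terms the time-matched baseline IOP" and covers only those two terms of the efficacy model.

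**The concern.** An analysis plan may change a protocol's tables, but the change should be declared and justified. Here the protocol's commitment is dropped without comment. For ocular adverse events, a programmer also has two instructions in SAP 11.1 that cannot both be followed.

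Pooling fellow eyes assumes that the arm has no bearing on the fellow eye. The fellow eye's own regimen is the same in every arm, but the patient's is not: controls have timolol in both eyes, while implant patients have timolol in one eye and the implant in the other. Under Protocol 5.6.1 and 8.8, nonstudy IOP-lowering medication in both eyes ends further administrations, sham included, and permits early exit from 12 months after the last one. If that occurs at different rates by arm, fellow-eye exposure and observation time differ too. By-arm columns would let a reader check the assumption; a pooled column cannot.

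The cornea is where this matters most. Corneal events are of special interest in SAP 11.1, and SAP 11.3.12 uses the fellow eye as the reference for study-eye endothelial loss.

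**Working it through.** **1. The texts side by side**

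| Item | Protocol | SAP |
|---|---|---|
| Ocular safety in general | By eye within dose strength (7.3.4), or dose strength or group (Summary) | Study eye by group, fellow eye pooled (11.0) |
| Ocular adverse events | Same rule | Pooled in one sentence of 11.1, by group and eye in another |
| Acuity, hyperemia, biomicroscopy/ophthalmoscopy/lens, cup/disc, pachymetry | Same rule | Fellow eye pooled |
| Endothelial cell density | Same rule | Fellow eye pooled; study-minus-fellow measure by group |
| Declared in SAP 17.0 | – | No |

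**2. What a pooled column can show**

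No figure in the plan bears on this point, so there is none to reproduce. The inputs are 1:1:1 allocation (Protocol 5.4) and about 510 patients, 170 per group (Protocol 7.7). Implant patients contribute 2 × 170 = 340 of the 510 fellow eyes, or two thirds.

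With equal arms, pooled rate = (p_control + p_10 + p_15) / 3. The rates below are assumptions, because the documents give none.

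- 10%, 10%, 10%: 30/3 = 10.0%
- 5%, 10%, 15%: 30/3 = 10.0%
- 2%, 14%, 14%: 30/3 = 10.0%
- 2%, 6%, 6%: 14/3 = 4.7%

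The first three patterns are indistinguishable in a pooled column.

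**3. What by-arm columns could show**

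The tables are descriptive, so this is only a guide. For 170 versus 170 and a two-sided 5% comparison, power = Φ{[|p1 − p2| − 1.96√(2p̄(1 − p̄)/170)] / √[(p1(1 − p1) + p2(1 − p2))/170]}.

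- 5% v 15%: (0.100 − 0.0638)/0.0321 = 1.13, power 87%
- 5% v 10%: (0.050 − 0.0560)/0.0284 = −0.21, power 42%

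By-arm columns would make a large difference plain and leave a moderate one uncertain.

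**4. What can be recovered for endothelial cell density**

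SAP 11.3.12 defines adjusted change = study-eye change − fellow-eye change, and summarises study-eye and adjusted change by arm and visit. If the same patients contribute to both, then in each arm:

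mean fellow-eye change = mean study-eye change − mean adjusted change.

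The mean is therefore recoverable. The counts of fellow eyes above a loss threshold are not. Take a patient whose study-eye loss S is at least 20% but under 30%, and whose adjusted loss A is at least 10% but under 20%. The fellow-eye loss is F = S − A. It exceeds 20 − 20 = 0% and is below 30 − 10 = 20%, so it may fall on either side of the 10% threshold. The study-eye and adjusted counts do not fix the fellow-eye count.

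**The case against.** The best defence is that all fellow eyes receive the same treatment, sham plus timolol twice daily (Protocol Table 7). Grouping eyes by the treatment that the eye actually received, as SAP 11.0 words it, is a coherent rule. Protocol 1.3.1 adds that systemic bimatoprost exposure in dogs was below quantitation at doses up to 60 µg, which makes a drug effect on the other eye less plausible. This stands as a rationale. It does not turn equal fellow-eye outcomes into a fact or replace a declaration in SAP 17.0.

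A reader might infer more than the documents support:

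- **That the fellow eye is an untreated eye.** It is not: it has sham and timolol in every arm.
- **That no difference between arms could be seen.** One sentence of SAP 11.1 plans by-group, by-eye event tables. Serious ocular events, and corneal and anterior chamber inflammation events, are by treatment group with no pooling stated. Mean endothelial change can be back-calculated.
- **That the adjusted endothelial measures depend on the pooling.** They do not: each patient's own fellow eye is subtracted and the result is shown by group. Dropping the pooling rule would leave them unchanged.
- **That all of SAP Section 11 is affected.** Visual field findings are by group with no pooling stated, implant size is for the study eye only, and iris color, macular OCT and AS-OCT are mainly listings.

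Table layouts are in a separate document (SAP 4.0) that is not available here. The conclusion therefore concerns the SAP's text.

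**Conclusion.** The departure is real. The SAP's general rule for fellow-eye safety differs from the protocol's, is not declared, and is contradicted within SAP 11.1. For parameters summarised only as pooled, no summary described in the SAP shows a between-arm fellow-eye difference. For endothelial cell density the gap is narrower: the mean per arm can be recovered if the same patients contribute, but the threshold counts cannot.

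This reads the pooling as running across all three arms. SAP 11.0 does not say so in those words, but identical fellow-eye treatment makes it the natural reading.

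The size of any hidden difference is unknown, and the rates above show only what pooling can mask. The affected tables are descriptive safety tables. Efficacy uses the study eye, so its analyses, the type I error rate and power do not change. The correction should be made, but no conclusion on efficacy depends on it.

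**What to change.** - Wherever SAP 11.0, 11.1, 11.3.2, 11.3.4 to 11.3.6, 11.3.11 and 11.3.12 pool the fellow eye, add fellow-eye columns for 10 µg, 15 µg and Control, by treatment actually received, as Protocol 7.1 specifies for the safety population. Keep the pooled column beside them if wanted.
- In 11.3.12, include the fellow-eye loss-threshold counts in the by-group columns.
- Reconcile the two statements on fellow-eye ocular adverse events in SAP 11.1.
- If any table stays pooled only, list it in SAP 17.0 as a change from the protocol and give the reason.

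The cost is SAP wording and a few extra columns in existing tables. No new data are needed, and nothing in the efficacy analysis or sample size changes.
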